8.2 Concurrent Therapies

The use of any concurrent medication, prescription or OTC, is to be recorded on the subject's source document and corresponding eCRF along with the reason the medication was taken.

Concurrent enrollment in another investigational drug or medical device study is not permitted.

8.2.1 Prohibited Medications/Treatments

Disallowed medications and treatments are listed in the Exclusion Criteria (Section 5.4). All medications and treatments that were not allowed prior to

study are also not allowed during the study, in particular no other dry eye treatment shall be used during the course of the study such as artificial tears (other than run-in medication), gels, ointments shall be used during the course of the study. Physical treatments such as lid scrubs, lid wipes, warm compresses must be kept stable. Hypochlorous acid wipes are not allowed.

8.2.2 Escape Medications

Not applicable.

8.3 Examination Procedures

8.3.1 Procedures to be Performed at Each Study Visit with Regard to Study Objective(s)

The procedures outlined in this section will performed as described in Appendix 2.

Visit 0 (Day -14 ± 2 days): Screening

- Informed consent / HIPAA
- Medical/medication history and demographic data
- Urine pregnancy test for females of childbearing potential
- Ocular Surface Disease Index (OSDI)
- Visual acuity (ETDRS)
- Slit-lamp biomicroscopy
- Fluorescein staining (NEI scale)
- Intraocular pressure
- Dilated fundoscopy
- Review of qualification criteria
- In-office instillation of run-in drops to qualified subjects
- Dispensation of subject diary and run-in for bilateral, BID dosing until Visit 1 as described in Section 7.1.3
- Adverse event query

[figure not shown]
• Qualified subjects are scheduled for Visit 1

Visit 1 (Day 1): Baseline / Randomization

- Collection and review of run-in and diary
 - Calculate subject compliance as described in Section 8.5
 - Ask subject if he/she dosed with run-in the morning of Visit 1 and, if applicable, record the time of the dose
- Medical/medication history update
- Adverse event query

٠	OSDI
٠	
•	Visual acuity Slit lamp biomicroscopy
i	Slit-lamp biomicroscopy
•	Fluorescein staining (NEI scale)
	Review of qualification criteria
•	Randomization
•	In-office instillation of randomized study drug
•	Dispensation of subject diary and randomized study drug for bilateral,
-	BID dosing until Visit 2 as described in Section 7.1.3
•	Adverse event query Randomized subjects are scheduled for Visit 2
Viait 1	
VISIU Z	(Day 15 ± 1): 2-Week Follow-Up
•	Collection and review of study drug and subject diary

[figure not shown]
- Medical/medication history update
- Adverse event query

[figure not shown]

- Adverse event query
- Schedule for Visit 4

Visit 4 (Day 57 ± 2): 8-Week Follow-Up

• Collection and review of study drug and subject diary

8.3.2 Early Termination/Discontinuations

If a subject is discontinued from the study before Visit 5 (Day 85 ± 2 days), then all safety evaluations that are to be performed at Visit 5 should be performed and the demographic data should be obtained on the day of early termination/discontinuation or at the discretion of the investigator.

Adverse events (both elicited and observed) will be monitored throughout the study. All AEs will be promptly reviewed by the investigator for accuracy and completeness. All AEs will be documented on the appropriate eCRF.

If a female has a positive pregnancy test during the study, then the investigator will notify immediately. The investigator shall request from the subject and/or the subject's physician copies of all related medical reports during the pregnancy and shall document the outcome of the pregnancy. The investigator will retain these reports together with the subject's source documents and will provide a copy of all documentation to **a**.

8.4 Schedule of Visits, Measurements and Dosing

8.4.1 Scheduled Visits

Refer to Appendix 1 for a schedule of visits and measurements.

8.4.2 Unscheduled Visits

An unscheduled visit may be performed during the course of the study to ensure subject safety. All procedures performed at an unscheduled visit will be recorded in the source documents and on the Unscheduled Visit eCRF pages. Any unscheduled visit procedure listed in the eCRF that is not performed should be indicated as "not done."

Evaluations that may be conducted at an Unscheduled Visit include

• Slit-lamp biomicroscopy;

- VA;
- IOP;
- Urine pregnancy test (for women of childbearing potential);
- Dilated fundoscopy;
- Assessment of AEs;
- Assessment of concomitant medications and/or treatments; and
- Any other assessments needed in the judgement of the investigator.

8.5 Compliance with Protocol

Subjects will be instructed on the proper use and storage of the study drug at Visits 0, 1, 2, 3, and 4, and provided with written instructions. Subject diaries and study drug will be collected at each visit from Visit 1 up to and including Visit 5 to assess subject compliance with the protocol.

8.6 Subject Disposition

8.6.1 Completed Subjects

A completed subject is one who has not been discontinued from the study.

8.6.2 Discontinued Subjects

Subjects may be discontinued prior to their completion of the study due to:

- AEs;
- Protocol violations;
- Lack of efficacy;
- Administrative reasons (e.g., inability to continue, lost to follow up);
- Sponsor termination of study;
- Pregnancy;
- Other

Note: In addition, any subject may be discontinued for any sound medical reason at the discretion of the investigator.

Notification of a subject discontinuation and the reason for discontinuation will be made to and/or study sponsor and will be clearly documented on the eCRF.

Discontinued subjects will not be replaced.

8.7 Study Termination

The study may be stopped at any time by the investigator, the sponsor, and/or with appropriate notification.

The whole trial may be discontinued prematurely in the event of any of new information leading to unfavorable risk-benefit judgment of the IP, e.g. due to:

- Occurrence of significant previously unknown adverse reactions or unexpectedly high intensity or incidence of known adverse reactions, or
- Other unfavorable safety findings.
- Sponsor's decision that continuation of the trial is unjustifiable for medical or ethical reasons.
- Poor enrollment of subjects making completion of the trial within an acceptable time frame unlikely.
- Discontinuation of development of the sponsor's IP.
- Health Authorities and IECs/ IRBs will be informed about the discontinuation of the trial in accordance with applicable regulations.

The whole trial may be terminated or suspended upon request of Health Authorities.

8.8 Study Duration

An individual subject's participation will involve 6 visits over approximately a 14week period. If applicable and as needed, after the study, subjects will be treated according to the standard of care by the discretion of the investigator / treating physician.

8.9 Monitoring and Quality Assurance

During the course of the study a monitor, or designee, will make routine site visits to review protocol compliance, assess study drug/device accountability, and ensure the study is being conducted according to the pertinent regulatory requirements. The review of the subjects' medical records will be performed in a manner that adequately maintains subject confidentiality. Further details of the study monitoring will be outlined in a monitoring plan.

Regulatory authorities of domestic and foreign agencies, sponsor quality assurance and or its designees may carry out on-site inspections and/or audits which may include source data checks. Therefore, direct access to the original source data will be required for inspections and/or audits. All inspections and audits will be carried out giving consideration to data protection as well as subject confidentiality to the extent that local, state, and federal laws apply.

9 ADVERSE EVENTS

9.1 Adverse Event

An adverse event (AE) is defined as any untoward medical occurrence associated with the use of a drug in humans, whether or not the event is considered drug-related. An AE can therefore be any unfavorable and unintended sign (e.g., an abnormal laboratory finding), symptom, or disease occurring after the subject started dosing with the study drug or the run-in medication, without any judgment about causality.

If there is a worsening of a medical condition that was present prior to the administration of the study drug, this should also be considered a new AE and reported. Any medical condition present prior to the administration of the study drug that remains unchanged or improved should not be recorded as an AE at subsequent visits.

Worsening of DED will be considered an AE only if the dry eye status of the subject exceeds their previous experiences with the condition. This will be determined by the subject and the investigator.

A clinically significant visual acuity decrease

from baseline (Visit 0) will be considered an AE.

Study drug includes the investigational drug under evaluation and any comparator drug, vehicle, or any other medications required by the protocol given during any stage of the study.

Documentation regarding the AE should be made as to the nature, date of onset, end date, severity, relationship to study drug, action(s) taken, seriousness, and outcome of any sign or symptom observed by the physician or reported by the subject upon indirect questioning.

9.1.1 Severity

Severity of an AE is defined as a qualitative assessment of the degree of intensity of an AE as determined by the investigator or reported to him/her by the patient/subject. The assessment of severity is made irrespective of relationship to investigational product or seriousness of the event and should be evaluated according to the following scale:

- *Mild*: Event is noticeable to the subject, but is easily tolerated and does not interfere with the subject's daily activities.
- *Moderate*: Event is bothersome, possibly requiring additional therapy, and may interfere with the subject's daily activities.
- *Severe*: Event is intolerable, necessitates additional therapy or alteration of therapy, and interferes with the subject's daily activities.

9.1.2 Relationship to Investigational Product

The relationship of each AE to the investigational product should be determined by the investigator using these explanations:

- *Suspected*: A reasonable possibility exists that the investigational product caused the AE.
- *Not Suspected*: A reasonable possibility does not exist that the investigational product caused the AE.

Suspected adverse reaction means any AE for which there is a reasonable possibility that the investigational product caused the AE. "Reasonable possibility" means there is evidence to suggest a causal relationship between the investigational product and the AE. Types of evidence that would suggest a causal relationship between the investigational product and the AE include: a single occurrence of an event that is uncommon and known to be strongly associated with IP exposure (e.g., angioedema, hepatic injury, Stevens-Johnson Syndrome); one or more occurrences of an event that is not commonly associated with IP exposure, but is otherwise uncommon in the population exposed to the IP (e.g., tendon rupture); an aggregate analysis of specific events observed in a clinical trial (such as known consequences of the underlying disease or condition under investigation or other events that commonly occur in the study population independent of drug therapy) that indicates those events occur more frequently in the IP-treatment group than in a concurrent or historical control group.

9.1.3 Expectedness

The expectedness of an AE should be determined based upon existing safety information about the study drug. CyclASol contains the active ingredient CsA and the vehicle F4H5 and has been tested in two clinical studies up to now, AEs of those have been listed in the investigator's brochure. Therefore, the following definition will be used:

- *Unexpected*: An AE that is not listed in the investigator's brochure (IB) in the Adverse Reaction Section at the specificity or severity that has been observed.
- *Expected*: An AE that is listed in the investigator's brochure (IB) in the Adverse Reaction Section at the specificity and severity that has been observed.
- *Not Applicable*: Any AE that is unrelated to the study drug.

The investigator should initially classify the expectedness of an AE, but the final classification is subject to the Medical Monitor's determination.

9.2 Serious Adverse Events

An AE is considered serious if, in the view of either the investigator or sponsor, it results in any of the following outcomes:

- Death;
- A life-threatening AE;
 - Note: An AE is considered "life-threatening" if, in the view of either the investigator or sponsor, its occurrence places the patient or subject at immediate risk of death. It does not include an AE that, had it occurred in a more severe form, might have caused death.
- Inpatient hospitalization or prolongation of existing hospitalization;
 - Note: The term "inpatient hospitalization" refers to any inpatient admission (even if less than 24 hours). For chronic or long-term inpatients, inpatient admission includes transfer within the hospital to an acute/intensive care inpatient unit. Inpatient hospitalization does not include: emergency room visits; outpatient/same-day/ambulatory procedures; observation/short stay units; rehabilitation facilities; hospice facilities; nursing homes; or clinical research/phase 1 units.
 - Note: The term "prolongation of existing hospitalization" refers to any extension of an inpatient hospitalization beyond the stay anticipated or required for the reason for the initial admission as determined by the investigator or treating physician.
- A persistent or significant incapacity or substantial disruption of the ability to conduct normal life functions;
 - Note: A serious adverse event (SAE) specifically related to visual threat would be interpreted as any potential impairment or damage to the subject's eyes (e.g., hemorrhage, retinal detachment, central corneal ulcer or damage to the optic nerve).
- A congenital anomaly/birth defect.

Important medical events that may not result in death, are life-threatening, or require hospitalization may be considered serious when, based upon appropriate medical judgment, they may jeopardize the patient or subject and may require medical or surgical intervention to prevent one of the outcomes listed in this definition.

9.3 **Procedures for Reporting Adverse Events**

All AEs and their outcomes must be reported to the study sponsor, and the IRB/IEC as required by the IRB/IEC, federal, state, or local regulations and governing health authorities and recorded on the appropriate eCRF.

[figure not shown]
9.3.1 Reporting a Suspected Unexpected Adverse Reaction

All AE that are 'suspected' and 'unexpected' are to be reported to the study sponsor and the IRB/IEC as required by the IRB/IEC, federal, state, or local regulations and governing health authorities.

9.3.2 Reporting a Serious Adverse Event

To ensure subject safety, all SAEs, regardless of relationship to the investigational product, must be immediately reported (i.e. within a maximum 24 HOURS after becoming aware of the event). All information relevant to the SAE must be recorded on the appropriate case report forms. The investigator is obligated to pursue and obtain information requested by and/or the sponsor in addition to that information reported on the case report form. All subjects experiencing a SAE must be followed up and the outcome reported.

In the event of a SAE, the investigator must notify and the sponsor immediately; obtain and maintain in his/her files all pertinent medical records, information, and medical judgments from colleagues who assisted in the treatment and follow-up of the subject; provide and the study sponsor with a complete case history, which includes a statement as to whether the event was or was not suspected to be related to the use of the investigational product; and inform the IRB of the AE within their guidelines for reporting SAEs.

Contact information for reporting SAEs:

9.4 **Procedures for Unmasking (if applicable)**

All subjects, investigators, and study personnel involved with the conduct of the study will be masked with regard to treatment assignments. When medically necessary, the investigator may need to determine what treatment arm has been assigned to a subject. When possible (i.e., in non-emergent situations), and/or the study sponsor should be notified before unmasking study drug.

If an investigator identifies a medical need for unmasking the treatment assignment of a subject, he/she should contact and/or the medical monitor prior to unmasking the identity of the IP, if possible. Will ask the site to complete and send them the Unmasking Request Form. Will notify Novaliq and jointly will determine if the unmasking request should be granted. They may consult the medical monitor as needed. The result of the request will be documented on the Unmasking Request Form. If approval is granted to unmask a subject, written permission via the Unmasking Request Form will be provided to the investigator. The investigator will unmask the subject using IWRS. The investigator will complete the Unmasking Memo form and include it in the subject's study file and provide a copy for the Trial Master File (TMF). For each unmasked request, the reason, date, signature, and name of the person who unmasked the subject, must be noted in the subject's study file.

Unmasked subjects will be discontinued from the study.

9.5 Type and Duration of the Follow-up of Subjects after Adverse Events

The investigator will follow unresolved AEs to resolution until the subject is lost to follow-up or until the AE is otherwise classified. Resolution means the subject has returned to baseline state of health or the investigator does not expect any further improvement or worsening of the AE. If the subject is lost to follow-up, the investigator should make 3 reasonable attempts to contact the subject via telephone, post, or certified mail. All follow-up will be documented in the subject's source document. Non-serious AEs identified on the last scheduled contact must be recorded on the AE eCRF with the status noted.

If the investigator becomes aware of any new information regarding an existing SAE (i.e., resolution, change in condition, or new treatment), a new SAE/Unanticipated Report Form must be completed and faxed to within 24 hours of the site's awareness of the new information. The original SAE form is not to be altered. The report should describe whether the event has resolved or continues and how the event was treated.

10 STATISTICAL HYPOTHESES AND METHODS OF ANALYSES

10.1 Analysis Populations

The following analysis population will be considered:

- Full Analysis Set (FAS) The FAS includes all randomized subjects who received at least one dose of investigation product. The primary analysis will be performed on the FAS. Subjects in the FAS will be analyzed as randomized.
- Per Protocol Set (PPS) The PPS includes subjects in the FAS who do not have significant protocol deviations and who complete the study. Protocol deviations will be assessed prior to database lock and unmasking. The PPS will be analyzed using observed data only for efficacy variables. Subjects in the PPS will be analyzed as treated.
- Safety Set (SAF) The SAF includes all randomized subjects who have received at least one dose of the investigational product. The SAF will be analyzed for all safety assessments. Subjects in the SAF will be analyzed as treated.

The statistical analysis of safety data will be performed for the SAF. The analysis of baseline and efficacy data will be performed for the FAS. The primary efficacy analyses will also be performed on the PPS as sensitivity analyses.

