10.4.3 Missing Data

The primary analysis will use the FAS with available data per subject. Additional robustness analyses will include repeating the primary analysis on the PPS; the FAS imputing missing data using LOCF; the FAS imputing missing data using Markov Chain Monte Carlo (MCMC) multiple imputation methodology under different assumptions of missingness (at random and not at random); and an analysis of trimmed means (Permutt et al., 2017).

No secondary efficacy endpoints or safety endpoints will be imputed.

10.4.4 Multiplicity Considerations

Fixed sequence testing will be employed to maintain the type I error rate. The primary analyses will first test the difference in the mean change from baseline corneal fluorescein staining (NEI scale) total score between treatments at Day 29. If the test of the difference is statistically significant at the two-sided alpha = 0.05 level in favor of CyclASol, then the study will be considered a success; CyclASol will be declared to be superior to vehicle in the mean change from baseline corneal fluorescein staining (NEI scale) total score at Day 29; and the difference in the mean change from baseline total OSDI score between treatments at Day 29 will be tested at the two-sided alpha = 0.05 level.

If in addition to a statistically significant test of the difference in the mean change from baseline corneal fluorescein staining (NEI scale) total score at Day 29 in favor of CyclASol, the test of the difference in the mean change from baseline total OSDI score at Day 29 is also statistically significant in favor of CyclASol, then CyclASol will be declared to be superior to vehicle in both the mean change from baseline corneal fluorescein staining (NEI scale) total score and the mean change from baseline total OSDI score at Day 29.

[figure not shown]

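### The per-protocol set for the Day 29 endpoints requires completion to Day 85, so events after Visit 3 can remove valid Day 29 data

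*Combined protocol and SAP*

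**What the plan says.** Section 10.1 states: "The PPS includes subjects in the FAS who do not have significant protocol deviations and who complete the study". It gives this set one visible task: "The primary efficacy analyses will also be performed on the PPS as sensitivity analyses". Section 10.4.3 likewise lists a repeat of the primary analysis on the PPS among the robustness analyses. Sections 6.1.1 and 10.4.5 place both primary endpoints, corneal staining and OSDI, at Day 29, which is Visit 3.

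The meaning of completion comes from elsewhere. Section 8.6.1: "A completed subject is one who has not been discontinued from the study". Section 8.3.2, on early termination, is framed by "If a subject is discontinued from the study before Visit 5", and the Synopsis makes Visit 5 (Day 85 ± 2 days) the study exit. Section 8.6.2 begins "Subjects may be discontinued prior to their completion of the study due to" and goes on to list adverse events, lack of efficacy and administrative reasons, among others. Section 9.4 adds: "Unmasked subjects will be discontinued from the study".

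The primary analysis itself is on another footing. Section 10.4.3: "The primary analysis will use the FAS with available data per subject". On deviations, Section 10.1 says: "Protocol deviations will be assessed prior to database lock and unmasking". The visible text does not say that only deviations up to Visit 3 count.

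**The concern.** The rule selects subjects on what happens after the endpoint has been measured. Nothing in Weeks 5 to 12 changes whether a subject followed the protocol up to Day 29, which is what a per-protocol check of a Day 29 endpoint should reflect. Some listed reasons for leaving (adverse events, lack of efficacy) can depend on treatment and on the Day 29 response itself; others (administrative reasons) need not. Unmasking after Day 29 leads to discontinuation and so to exclusion. A significant deviation that occurs only after Visit 3 can have the same effect. Masked review of deviations prevents selective classification, but it sets no time limit, and completion is a criterion that such review cannot adjust.

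What is at stake is the reading of the PPS result. If FAS and PPS differ, the difference mixes adherence to Day 29 with later attrition. If they agree, the agreement says less about adherence than it appears to.

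**Working it through.** **1. What the sections imply together.** PPS membership requires completion (10.1). Completion means no discontinuation (8.6.1). Discontinuation can occur at any time before Visit 5, Day 85 (8.3.2). The PPS is applied to Day 29 endpoints (10.1, 10.4.3, 10.4.5). So a subject with a Day 29 value who leaves between Visits 3 and 5 is in the FAS analysis and out of the PPS analysis. No visible passage defines a separate Day 29 PPS.

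**2. The plan's own figures.** Inputs from Section 10.3 and the Synopsis: 142 per arm, two-sided alpha 0.05; staining difference -0.85, SD 2.2; OSDI difference -5.0, SD 14.5; dropout 10%. The two-sample t-test has power 90.1% for staining (stated 90%) and 82.5% for OSDI (stated 82%). Enrolment: 142 / 0.9 = 157.8, rounded up to 158 per arm, 316 in total. All reproduce.

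**3. How many subjects the completion rule removes.** Expected dropouts: 316 × 0.10 = 31.6. The documents do not give their timing, so the share falling after Day 29 is an assumption, shown over its full range.

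| Share of dropout after Day 29 | Subjects removed |
|---|---|
| none | 0 |
| one third | 31.6 × 1/3 = 10.5, about 11 |
| one half | 31.6 × 1/2 = 15.8, about 16 |
| uniform over Days 1 to 85 | 31.6 × 56/84 = 21.1, about 21 |
| all | 31.6, about 32 |

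The zero row is compatible with the sizing: 316 × 0.9 = 284.4, which matches 2 × 142 = 284 subjects for the Day 29 tests. Exclusions for later deviations would come on top and cannot be counted from the documents.

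**4. Possible shift in the staining difference.** Let p be the proportion of subjects with Day 29 data in an arm who leave later, and d the amount by which they are worse at Day 29 than those who stay. Removing them lowers that arm's mean by p × d, so the shift in the difference (active minus vehicle) is (p_vehicle − p_active) × d. The documents supply neither p by arm nor d; all values below are assumptions.

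| Late exit, vehicle / active | d | Shift | Difference in PPS |
|---|---|---|---|
| 6% / 6% | 2 | 0 | -0.85 |
| 8% / 4% | 2 | 0.04 × 2 = +0.08 | -0.77 |
| 4% / 8% | 2 | -0.04 × 2 = -0.08 | -0.93 |
| 8% / 4% | 1 | +0.04 | -0.81 |
| 4% / 8% | 1 | -0.04 | -0.89 |

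The standard error at 142 per arm is 2.2 × √(2/142) = 0.261. The unbalanced shifts are 0.04 / 0.261 = 0.15 and 0.08 / 0.261 = 0.31 standard errors, in either direction.

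**5. Power of the supportive analysis.** At the upper bound, all 158 per arm have Day 29 data and the rule reduces them to 142. Without bias, power falls from 92.8% to 90.1% for staining and from 86.3% to 82.5% for OSDI.

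**The case against.** The strongest reply is that little depends on the PPS. The success rule never uses it, the FAS keeps every late leaver's Day 29 value, and the PPS stands beside LOCF, multiple imputation, trimmed means, t-tests, Wilcoxon tests and repeated-measures models. That is right, and it limits how serious the point can be.

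The sizing also fits a reading in which all 10% is lost before Day 29, so that the rule removes nobody. That reading is possible, but nothing in the plan says dropout stops at Day 29, and 56 of the 84 treatment days follow it.

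The power comparison starts from 158 per arm, which the plan never claims; even at the upper bound the PPS keeps 142 per arm and the planned power, before exclusions for deviations. This stands: loss of power is not the reason to change the rule. The late-exit rates and deficits are assumed, and the one visible withdrawal figure, 1.4% leaving Phase 2 treatment for an ocular adverse event (Section 1.4), gives no support to a large imbalance from that cause. This also stands, although that figure excludes other reasons.

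Finally, the document is heavily redacted. A time limit on deviations, or a later endpoint needing a completer set, may lie in hidden text. The deviation part therefore rests on the visible wording only. The completion part does not: the visible text applies this one set to Day 29.

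**Conclusion.** The point holds. As written, the PPS can drop valid Day 29 values because of events after Day 29, some of which may be related to treatment or response. The primary FAS test, the fixed sequence, type I error and the sample size are unaffected. The completion rule costs 0 to about 32 subjects with Day 29 data at the planned dropout rate, depending on timing that the documents do not give. In the scenarios tried, the staining difference moves by no more than 0.08 points (0.31 standard errors), in a direction that cannot be known in advance, and not at all if late exit is balanced. The case for change rests on interpretability more than on size: an FAS/PPS difference could not be attributed to adherence alone. It should be corrected, but it does not threaten the main conclusion.

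**What to change.** In Section 10.1, define the PPS for the Day 29 analyses as FAS subjects who have a Visit 3 assessment of the endpoint in question and no significant protocol deviation up to and including Visit 3, regardless of later discontinuation. If a Day 85 per-protocol analysis is wanted, define a separate completer set for it.

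The cost is one sentence and one additional population flag. Both must be in place before database lock and unmasking, since a later change to the set would look post hoc. The primary analysis, alpha and sample size stay as they are.
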